7.3 Secondary Outcomes Analysis

The mean change, from baseline to 7 days, in the Modified Harris mucositis-related pain assessment tool scores and the mean change in oral functioning scores will be compared between study arms, utilizing ANOVA or Kruskal-Wallis test (eat, swallow, talk: unable=2, difficulty=1, able=0. Oral functioning score is the total score of 3 categories, ranged 0-6). We will also determine if there are any differences between arms in presence or absence of pain, pain scores, overall analgesic use (including opiate use primarily used for oral mucositis pain via MEDD measurement), and the incidence of untoward side effects utilizing ANOVA, Kruskal-Wallist, Chi-square test, or Fisher's exact test as appropriate. In addition, to obtain a measure of compliance with MB treatment, we will compare the dropout rate within the MB group to the dropout rate in the conventional therapy group utilizing Chi-square test or Fisher's exact test.

The Investigator is responsible for completing an efficacy/safety summary report and submitting it to the IND office Medical Monitor for review. This should be submitted after the first 5 evaluable patients per arm, complete 7 days of study treatment, and every 5 evaluable patients per arm, thereafter.

In addition, the Patient Drug Administration log will be used to keep the record of drug usage. Duration of pain relief corresponding to each drug use will be collected during the interview, in person for Day 0 and via telephone for Day 1, Day 2, and Day 7. The number of MB doses needed (during the last 24 hours or since the last follow-up) in order to achieve pain relief will be collected on Day 1, Day 2, and Day 7.

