2.0 Study Objective

The primary objective is to evaluate the efficacy of MB in reducing the severity of mucositis-related pain, measured by Numeric Rating Scale (NRS), in cancer patients who underwent or are undergoing chemotherapy or radiation therapy. Patients will be randomized to one of 4 intervention arms, including conventional therapy and conventional therapy plus MB with one of 3 concentrations (0.025%, 0.05% or 0.1%) oral rinse to swish and spit.

2.1 Primary Outcomes:

Oral mucositis pain reduction (measured by using the Numeric Rating Scale (NRS); from 0, representing no pain, to 10, representing the worst possible pain) from baseline to 7 days post treatment. The pain scale is included in the Modified Harris mucositis-related pain assessment tool.

2.2 Secondary Outcomes:

1. Oral functioning (eat, swallow, talk: unable=2, difficulty=1, able=0. Oral functioning score is the total score of 3 categories, ranged 0-6). Scale is included in the Modified Harris mucositis-related pain assessment tool. Measurements are obtained at day 0, 1, 2, and 7.
2. Presence of absence of pain and pain score measured by NRS at day 0, 1, 2, and 7.
3. Number of MB doses needed to achieve pain relief at 0, 1, and 2 days post MB administration
4. Morphine equivalent daily dose (MEDD) used for oral mucositis pain at 2, and 7 days post MB administration.
5. Incidence of untoward side effects immediately after MB administration and at 1, 2, 7 days post MB administration.

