4.0 Study Design

This study is a prospective, randomized trial involving adult patients with intractable pain associated with oral mucositis. This study will have four intervention arms - MB 0.025 arm, MB 0.05 arm, MB 0.1 arm and a control arm. MB arm will receive one of 0.025%, 0.05% or 0.1% MB solution in addition to conventional therapy (0.025%, 0.05%, and 0.1% MB solution for MB 0.025, MB 0.05, and MB 0.1 arm, respectively), and the control arm will receive conventional therapy for 2 days, then will receive one of 3 solutions which will be randomly selected if they would like to receive MB solution.

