6.3 Patient randomization and assignment to treatment arm

The study will accrue up to 60 patients with a 1:1:1:1 ratio to include 4 intervention arms. Those include conventional therapy, conventional therapy + MB 0.025%, conventional therapy + MB 0.05%, and conventional therapy + MB 0.1%; each group will include 15 patients. We will conduct stratified randomization by baseline pain (baseline NRS 0-5 vs. 6-10) and oral functioning score (0-3 vs. 4-6). The primary endpoint is the reduction in pain score from baseline to 7 days. Patient randomization will be done through the Clinical Trial Conduct website. Study staff will be uninvolved in the randomization process.

Once a patient is enrolled in the study, the Investigational Pharmacy at MDACC retrieves the randomized treatment arm information from the Clinical Trial Conduct website. Once a patient is randomized to a treatment arm, Investigational Pharmacy will relay the information to the dispensing pharmacy at MDACC.

Study staff will contact patients either in person if as an inpatient or by phone at every follow-up the encounter to check for adverse events during routine patient encounters or via telephone calls.

Patients who were randomized to conventional arm will have an option to cross over to one of 3 MB arms, which they will be randomly allocated to, after completing 2 day pain measurements.

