6.5 Data collection

Patients enrolled in the study will be asked to complete a baseline assessment questionnaire in person, including the Modified Harris mucositis-related pain assessment tool. The patient will have subsequent follow-up interviews at 1, 2, 7 days with repeat assessment of the Modified Harris mucositis-related pain assessment tool. Furthermore, on Baseline, Day 0, Day 1, Day 2, Day 7 and Day 30, adverse event will be assessed, and this maybe by telephone or face-to-face in the clinic. The patient's medication use will also be assessed at follow-up, including morphine equivalent daily dose (MEDD) and other reported analgesics used for the treatment of their mucositis-related pain. Lastly, the research team will investigate if any patient reported any side effects from the treatment.

All completed data will be stored electronically in the MD Anderson REDCap system, in a locked file, on password-protected computers. Only research team members will access the files. Subject registration will be entered into CORe database.

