7.2 Primary Outcome Analysis

Descriptive statistics (means (SDs) or counts (percent)) will be used to summarize demographics, disease, and treatment variables according to the intervention arm. Potential differences between the arms based on demographic, disease, and treatment variables will be explored using Chi-square test or Fisher's exact test for categorical variables and ANOVA or Kruskal-Wallis test for continuous variables, depending upon the nature of the variables being investigated.

Our primary endpoint is the reduction in pain scores assessed within the NRS component of the Modified Harris mucositis-related pain assessment tool from baseline to 7 days which is considered the end of the study. The mean change in scores will be compared among 4 arms, utilizing ANOVA. If there are significant differences between intervention arms in some covariates, a linear regression model will be utilized to compare arms by adjusting for those significant covariates. The mean pain scores over time will be compared among study arms, utilizing linear mixed effects models. Covariates that showed significant differences among study arms will be adjusted in the linear mixed effects models. Two separate analyses, intention to treat and per protocol, will be conducted for primary analysis. Tukey's pairwise comparison will be conducted if a significant difference is observed among 4 arms. Intention to treat analysis population will include all patients who were randomized to one of treatment groups regardless of completion of the treatment. Per protocol analysis will include those patients who completed the treatment originally allocated. Patients who did not have 7day NRS will be replaced.

Patients who were initially enrolled in conventional arm and crossed over to one of MB arms will be included in assigned MB arm.

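### Section 7.3 prespecifies no comparison of oral functioning at Days 1 and 2, the only follow-up visits before controls may take methylene blue, and crossover compromises the Day 7 comparison

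*Combined protocol and SAP*

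**What the plan says.** **Collection.** Section 2.2 lists oral functioning (eat, swallow and talk, total 0–6) first among the secondary outcomes and adds: "Measurements are obtained at day 0, 1, 2, and 7". Section 6.5 agrees: "The patient will have subsequent follow-up interviews at 1, 2, 7 days with repeat assessment of the Modified Harris mucositis-related pain assessment tool". The oral functioning scale is part of that tool.

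**Analysis.** Section 7.3 compares between arms, by ANOVA or Kruskal-Wallis, "The mean change, from baseline to 7 days, in the Modified Harris mucositis-related pain assessment tool scores and the mean change in oral functioning" scores. It then gives a further list: "We will also determine if there are any differences between arms in presence or absence of pain, pain scores, overall analgesic use", followed by side effects. Oral functioning is not in that list. The only analysis across visits is in Section 7.2, and it concerns pain: "The mean pain scores over time will be compared among study arms, utilizing linear mixed effects models".

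**Crossover.** Section 4.0 says that "the control arm will receive conventional therapy for 2 days, then will receive one of 3 solutions which will be randomly selected", if the patient wishes. Section 6.3 confirms that this is a choice, available once the Day 2 pain measurements are complete: "Patients who were randomized to conventional arm will have an option to cross over to one of 3 MB arms". The last paragraph of Section 7.2 counts a control who crosses over in the MB arm that the patient moves to. Section 7.3 has no crossover rule of its own.

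**The concern.** Section 7 opens by asking whether MB added to conventional care differs from conventional care alone. For oral functioning, the visits that can answer this with all randomised controls unexposed are Days 1 and 2. The plan collects data at both and names no comparison at either. The one time it does name falls after controls have been free to take MB for up to five days (7 − 2).

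Crossover could be common. Section 5.2 enrols patients who still have pain and oral dysfunction despite conventional therapy, and the option is open to every control. If the plan is followed as written, the reported result would be either a non-randomised comparison or a diluted one. Any Day 2 result added later would be post hoc.

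**Working it through.** **1. The plan's own figure.** The only power statement (Sections 5.1 and 7.1) is for the primary pain outcome: 15 per arm, mean reductions 0, 2, 2.5 and 3, SD 2.5, alpha 0.05, power 83%.

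- Grand mean = 7.5/4 = 1.875.
- Sum of squared deviations = 3.516 + 0.016 + 0.391 + 1.266 = 5.1875.
- SD of the means = √(5.1875/4) = 1.139 (stated 1.14).
- Noncentrality λ = 15 × 5.1875/2.5² = 12.45, with 3 and 56 degrees of freedom. Power = 82.7%, which reproduces the stated 83%.

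This figure is not in dispute. The documents give no effect size, SD or power for oral functioning.

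**2. Visit by visit.**

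| Visit | Oral functioning recorded | All randomised controls without MB | Comparison named |
|---|---|---|---|
| Day 1 | yes | yes | none |
| Day 2 | yes | yes | none |
| Day 7 | yes | no, crossover optional | change from baseline |

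Section 6.3 ties crossover to the Day 2 pain measurements. Pain and oral functioning are in the same tool, so the Day 2 oral functioning score also precedes crossover, assuming that the tool is completed in one interview.

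**3. Day 7 if crossovers move to the MB arms.** Let s be the share of controls who cross; the documents give no value. Controls remaining = 15 × (1 − s): 11.25, 7.5 and 3.75 for s = 25%, 50% and 75%, or about 11, 8 and 4, and none at s = 100%. Those who remain chose to remain. If patients who are improving decline MB, the remaining controls look better than the randomised arm. If the sickest decline it, they look worse. The direction of bias cannot be known in advance.

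**4. Day 7 if crossovers stay as randomised.** Assume that each crosser gains the full average MB effect D. The control mean rises by sD, so the observed difference is D − sD = (1 − s)D: 75%, 50% and 25% of D for the same three shares. If crossers gain only part of the effect by Day 7, the dilution is smaller.

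**5. Illustration of step 4 on the pain inputs.** With D = (2 + 2.5 + 3)/3 = 2.5, control mean 2.5s and SD held at 2.5:

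| s | Control mean | MB minus control | λ | Power |
|---|---|---|---|---|
| 0 | 0 | 2.5 | 12.45 | 82.7% |
| 25% | 0.625 | 1.875 | 7.53 | 59.1% |
| 50% | 1.25 | 1.25 | 4.01 | 33.7% |
| 75% | 1.875 | 0.625 | 1.90 | 17.4% |
| 100% | 2.5 | 0 | 1.20 | 12.4% |

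At s = 100% the remaining power reflects differences between concentrations only. The table shows the mechanism on a 0–10 pain scale. It is not a power estimate for oral functioning.

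**The case against.** **The time in Section 7.3 is ambiguous.** Grammatically, baseline to 7 days belongs to the tool scores, and the change in oral functioning carries no time of its own. A reader might infer that the plan analyses Day 7 only and throws the early data away. The text does not establish that: the data are collected, and the time point could be called unspecified. Day 7 is still the natural reading, because the scale is part of the tool. On either reading no Day 1 or Day 2 comparison is prespecified, so the gap stands.

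**The direction of bias is not settled.** A reader might infer that Day 7 is simply biased toward no difference. That holds only if crossovers stay as randomised and benefit from MB. The written rule in Section 7.2 moves them, and Section 7.3 neither adopts nor replaces it.

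**Crossover is a wider problem.** It also affects pain and the other Day 7 outcomes. This is true, but pain already has a model over time in Section 7.2. Correcting the pain analysis would not supply an early comparison of oral functioning.

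**Day 2 is not free of other bias.** Section 5.0 blinds the concentration only, no placebo rinse is described, and patients report the score themselves. Section 7.2 also replaces patients without a Day 7 pain score, which could remove randomised patients from a Day 2 comparison. Both points stand. The fix deals with the second and not with the first.

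**Day 2 asks a different question.** Moving from a 7-day to a 2-day effect is a real change, and the primary endpoint is set at Day 7. This stands as a reason to keep Day 7 in the report.

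**Conclusion.** The point holds in this form: Section 7.3 prespecifies no pre-crossover comparison of oral functioning, and the Day 7 comparison with conventional therapy is compromised under either handling of crossovers. With crossovers moved, randomisation is lost, about 11, 8 or 4 of 15 controls remain at assumed crossover shares of 25%, 50% or 75%, and the bias has unknown direction. With crossovers kept as randomised, 75%, 50% or 25% of the difference remains, provided that each crosser gains the full MB effect. The share crossing over is an assumption throughout.

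Two stronger conclusions are tempting and not supported. One is that the power losses illustrated on the pain scale apply to oral functioning; the documents give no inputs for that outcome. The other is that Day 2 must replace Day 7 altogether; the documents set the trial's main horizon at 7 days, and an added contrast is enough. The stated sample size is unaffected. This is one secondary outcome without a power statement, so the change is advisable and not critical.

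**What to change.** In Section 7.3:

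- Add a prespecified comparison of baseline-to-Day-2 change in oral functioning, by arm as randomised and adjusted for the baseline score. A repeated-measures model over Days 1, 2 and 7 with a Day 2 contrast would serve equally well.
- Base the conclusion on MB versus conventional therapy for this outcome on that pre-crossover contrast.
- Keep every randomised patient with Day 2 data in it, including those without a Day 7 pain score who are replaced under Section 7.2.
- State the time point for the existing oral functioning comparison, and report Day 7 by randomised arm, labelled as post-crossover.

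The cost is a change of wording and one extra analysis, with no new visits or data. The downside is that the pre-crossover contrast speaks to a 2-day and not a 7-day effect, and the report should say so.

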8.0 Adverse Events Reporting

8.1 Adverse Events (AEs)

All patients will be monitored through weekly in person or by phone calls by the research staff allowing for close monitoring of potential adverse events during treatment. In addition, patients will be given a contact phone number for treatment-related questions.

Research staff will collect toxicity, symptoms, and adherence to study medication schedule weekly. Treatment-related toxicities (NCI Common Terminology Criteria for Adverse Events, version 4) will be monitored by the research staff.

Grade 1 and Grade 2 AEs will not be reported. AEs that are Grade 3 and above that meet the definition for serious adverse events (SAEs) in Section 8.2 will be considered to be serious adverse events (SAEs) and will be reported. SAEs that are unexpected and related (definitely, probably, or possibly related) to MB use will be reported promptly according to institutional policies (see below). SAEs that are either expected or unexpected but unrelated (unrelated or unlikely to be related) to MB use will be summarized on the continuing review report. The principal investigator and the treating physician will determine whether or not an AE is related to the study medication.

If in the course of assessing symptoms, the patient reports severe symptoms, the data collector will determine if the patient's healthcare provider is aware that the patient is experiencing this severe symptom. If the healthcare provider is not aware, the data collector will determine if the patient intends to inform the healthcare provider of the symptom and its severity within 24 hours. If the patient does not intend to inform the health care provider, the data collector will inform the patient that the data collector will let the health care provider know of the severity of the symptom within 24 hours. If in the course of assessing symptoms, the data collector becomes aware of any imminently life-threatening condition that the patient is experiencing, the data collector will let the patient know that data collector will be informing a healthcare provider immediately of the condition. The data collector will then initiate contact with a healthcare provider immediately.

A list of adverse events known to be associated with primary treatment is listed in section 3.2 of the protocol.

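### Trial dropout, compared between MB and conventional therapy, is used to measure compliance with MB; it does not measure rinse use, and the crossover rule could distort it if carried over

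*Combined protocol and SAP*

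**What the plan says.** Section 7.3 sets out the compliance measure in one sentence: "we will compare the dropout rate within the MB group to the dropout rate in the conventional therapy group". The planned test is chi-square or Fisher's exact. Dropout is not defined, and neither the grouping of crossovers nor the counting of replaced patients is stated there.

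Other parts of the plan bear on this:

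- **Use of the rinse (section 6.4).** Patients rinse until pain resolves or the 100 mL is finished; the supply is expected to last two to three days with regular use.
- **Usage data.** Section 7.3 says that "the Patient Drug Administration log will be used to keep the record of drug usage", and dose counts are taken on Days 1, 2 and 7. Section 8.1 adds: "Research staff will collect toxicity, symptoms, and adherence to study medication schedule weekly". No compliance summary of these data is specified.
- **Crossover (section 6.3).** Controls may move to one of the MB arms, "which they will be randomly allocated to, after completing 2 day pain measurements".
- **Grouping (section 7.2).** Controls who "crossed over to one of MB arms will be included in assigned MB arm". The same section says: "Intention to treat analysis population will include all patients who were randomized to one of treatment groups regardless of completion of the treatment".
- **Replacement (section 7.2).** "Patients who did not have 7day NRS will be replaced".

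**The concern.** There are two separate problems.

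The first follows from the text alone. A patient can skip rinses and still give a Day 7 score. A patient can also stop rinsing as instructed because pain has gone, or finish the supply by Day 3 and leave on Day 5 having complied fully. Dropout misclassifies all of these. A test against conventional therapy cannot help, since that arm has no rinse to take.

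The second is conditional. If crossovers are counted as MB for this comparison, a control lost before Day 2 can count only against conventional therapy, while a control retained to Day 2 may move into the MB denominator. Membership of a group then depends partly on having stayed, which is a form of immortal-time bias.

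At stake is any statement in the trial report about adherence to, or retention on, MB. The primary endpoint result does not depend on this comparison.

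**Working it through.** **The plan's own figures.** The documents give no dropout, crossover or compliance figure to reproduce. The one nearby figure, 83% power for 4 × 15 patients, does reproduce: noncentrality 15 × 5.1875 / 2.5² = 12.45 on 3 and 56 df gives 82.7%. This point does not affect it.

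**Inputs from the documents.** 15 conventional and 45 MB patients (section 6.3, 1:1:1:1 of 60); crossover only after the Day 2 measurements (6.3); crossovers counted as MB (7.2, if applied to 7.3).

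**Assumed inputs.** The same true dropout d in every arm; d2 = dropout before Day 2; d7 = later dropout among those retained, so d7 = 1 − (1 − d)/(1 − d2); c = share of retained controls who cross over, unrelated to later dropout. Ranges: d of 10 to 30%; early share of 0, 2/7 or 1/2; c up to 100%.

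**Formulas.**
- Conventional rate = [d2 + (1 − d2)(1 − c)d7] / [d2 + (1 − d2)(1 − c)]
- MB rate = [45d + 15(1 − d2)c·d7] / [45 + 15(1 − d2)c]

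**Worked case, d = 20%, 2/7 early.** d2 = 0.0571 and d7 = 1 − 0.80/0.9429 = 0.1515.
- c = 50%: conventional 1.93/7.93 = 24.3%; MB 10.07/52.07 = 19.3%.
- c = 80%: conventional 1.29/3.69 = 34.9%; MB 10.71/56.31 = 19.0%.

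**Range (conventional vs MB).**

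| True dropout | Share before Day 2 | c = 50% | c = 80% |
|---|---|---|---|
| 10% | 2/7 | 12.5% vs 9.6% | 19.2% vs 9.5% |
| 20% | 0 | 20% vs 20% | 20% vs 20% |
| 20% | 2/7 | 24.3% vs 19.3% | 34.9% vs 19.0% |
| 20% | 1/2 | 27.3% vs 18.8% | 42.9% vs 18.3% |
| 30% | 2/7 | 35.5% vs 29.1% | 47.9% vs 28.7% |

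**False rejection.** In 8,000 simulated trials per scenario, with d = 20% and 2/7 early, Fisher's test at 0.05 rejects in about 5% (c = 50%) and 9% (c = 80%), almost always favouring MB. By randomised arm it rejects in about 2 to 4% across the scenarios.

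**Reversal.** Take d2 = 2%, c = 50%, and later dropout of 5% in controls who stay and 25% in those who cross. True dropout is 0.02 + 0.98 × 0.15 = 16.7% in every arm. The analysed rates are 0.67/7.65 = 8.7% conventional and 9.35/52.35 = 17.9% MB, so the bias now runs against MB.

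**The case against.** The crossover rule stands under the primary analysis. Section 7.3 does not adopt it, and section 7.2 also defines an intention-to-treat population of everyone randomised. So the grouping for dropout is unspecified, not shown to be biased. That stands, and it is why the second problem is put conditionally.

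A reader might infer that the crossover rule necessarily produces a retention advantage for MB, and a large one. The documents do not support this. Starting from 3/15 and 9/45 dropouts (20% each), moving 8 controls gives 3/7 (43%) versus 9/53 (17%), and moving 10 gives 3/5 (60%) versus 9/55 (16%), Fisher p = 0.0499. But these figures require that all dropout falls before Day 2 and that no crossover ever leaves. With 2/7 of a 20% dropout early, the same crossover shares (8 of 12 and 10 of 12) give about 28% versus 19% and 38% versus 19%. If one of the three control dropouts is instead a crossover who leaves later, the second table becomes 2/5 versus 10/55, p = 0.26.

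It is also tempting to say that replacement removes dropouts from the count. Section 7.2 does not say so; how they are counted is simply unstated.

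Finally, the comparison is not among the five secondary outcomes in section 2.2, and dose counts are listed there. Both points limit the consequence. However, those counts concern doses needed for pain relief, and no compliance measure is derived from them.

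**Conclusion.** The point holds in two parts of different strength. That between-group dropout is the wrong measure of MB compliance is certain from the text and needs no assumption. That the comparison may also be distorted depends on carrying the section 7.2 crossover rule into section 7.3, and its size depends on rates the documents do not give. In the worked case the expected spurious gap is about 5 percentage points at 50% crossover and 16 at 80%, with the analysed conventional group falling from 15 to about 8 or 4 patients. The direction favours MB only if some controls leave before Day 2 and crossing over is unrelated to later dropout. The remedy is cheap, so it is worth making, although this is a supporting analysis.

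**What to change.** 1. **Compliance.** Drop the between-group test as a compliance measure. Among MB recipients, describe rinses taken (from the administration log) against rinses due up to pain resolution or end of supply, so that a stop for resolved pain is not counted as non-compliance. Show crossovers separately.
2. **Reconcile first.** Rinses due cannot be defined yet. Section 6.4 gives both a six-hourly interval (24/6 = 4 a day) and a total of three a day. Uses per 100 mL are 6 to 10 in sections 3.1 and 6.4 but 4 to 6 in section 3.2, while 100 mL at 6 to 10 mL per rinse is 10 to about 17. The sponsor must reconcile these statements.
3. **Dropout.** Define it, compare it by randomised arm, keep replaced patients in numerator and denominator, and report it before and after Day 2.
4. **Returned volume.** Do not rely on it. Section 6.4 returns unused MB for incineration without saying that it is measured, and with rinses of 6 to 10 mL, 60 mL used could mean 6 to 10 rinses.

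The cost is analysis-plan wording plus the reconciliation in item 2. The log and adherence data are already to be collected.
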